#### Confirming Progression

Unlike RECIST 1.1, iRECIST requires the confirmation of progression and uses the terms iUPD (unconfirmed progression) and iCPD (confirmed progression). Confirmatory scans should be performed at least 4 weeks, but no longer than 8 weeks after iUPD.

In the context of confirmation of PD per iRECIST, and the timeline of confirmatory scans to be performed at least 4 weeks, but no longer than 8 weeks after iUPD, it should be specifically noted that in case of any signs of rapidly progressing disease establishment of PD and a following therapy switch should be made also earlier than 4-8 weeks after iUPD when necessary.

iCPD is confirmed if further increase in tumor burden, compared to the last assessment, is seen as evidenced by one or more of the following:

- Continued increase in tumor burden (from iUPD) where RECIST 1.1 definitions of progression had been met (from nadir) in target, non-target disease or new lesions
  - Progression in target disease worsens with an increase of at least 5 mm in the absolute value of the sum
  - Continued unequivocal progression in non-target disease with an increase in tumor burden
  - Increase in size of previously identified new lesion (s) (an increase of at least 5 mm in the absolute value of the sum of those considered to be target new lesions) or additional new lesions.
- RECIST 1.1 criteria are met in lesions types (target or non-target or new lesions) where progression was not previously identified, including the appearance of additional new lesions.

[figure not shown]
If iUPD is not confirmed at the next assessment, then the appropriate response will be assigned (iUPD if the criteria are still met, but no worsening, or iSD, iPR or iCR if those criteria are met compared to baseline). As can be seen in [Table 8](#) and [Table 9](#), the prior documentation of iUPD does not preclude assigning iCR, iPR, or iSD in subsequent time-point assessments or as best overall response (BOR) providing that iCPD is not documented at the next assessment after iUPD.

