**Table 8 : Time-point iRESPONSE**

Target Lesions*	Non-Target Lesions*	New Lesions*	Time Point Response	
			No prior iUPD**	Prior iUPD***, ***
iCR	iCR	No	iCR	iCR
iCR	Non-iCR/Non-iUPD	No	iPR	iPR
iPR	Non-iCR/Non-iUPD	No	iPR	iPR
iSD	Non-iCR/Non-iUPD	No	iSD	iSD
iUPD with no change OR decrease from last TP	iUPD with no change OR decrease from last TP	Yes	NA	NLs confirms iCPD if NLs were previously identified and increase in size ( $\geq 5$ mm in SOM for NLT or any increase for NLNT) or number. If no change in NLs (size or number) from last TP, remains iUPD
iSD	iUPD	No	iUPD	Remains iUPD unless iCPD confirmed based in further increase in size of NT disease (need not meet RECIST 1.1 criteria for unequivocal PD)
iUPD	Non-iCR/Non-iUPD	No	iUPD	Remains iUPD unless iCPD confirmed based on: 
 
○ further increase in SOM of at least 5 mm, otherwise remains iUPD
 

iUPD	iUPD	No	iUPD	Remains iUPD unless iCPD confirmed based on further increase in: 
 
○ previously identified T lesion iUPD SOM <math>\geq 5</math> mm and / or
 
○ NT lesion iUPD (prior assessment - need not be unequivocal PD)
 

iUPD	iUPD	Yes	iUPD	Remains iUPD unless iCPD confirmed based on further increase in: 
 
○ previously identified T lesion iUPD <math>\geq 5</math> mm and / or
 
○ previously identified NT lesion iUPD (need not be unequivocal) and / or
 
○ size or number of new lesions previously identified
 

Non-iUPD/PD	Non-iUPD/PD	Yes	iUPD	Remains iUPD unless iCPD confirmed based on 
 
○ increase in size or number of new lesions previously identified
 

\* Using RECIST 1.1 principles. If no PSPD occurs, RECIST 1.1 and iRECIST categories for CR, PR and SD would be the same. \*\* in any lesion category. \*\*\* previously identified in assessment immediately prior to this TP.

All patients will have their iBOR from the start of study treatment until the end of treatment classified as outlined below.

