**Table 9 : iRECIST best overall response**

TPR1	TPR2	TPR3	TPR4	TPR5	iBOR
iCR	iCR, iPR, iUPD, NE	iCR, iPR, iUPD, NE	iUPD	iCPD	iCR
iUPD	iPR, iSD, NE	iCR	iCR, iPR, iSD, iUPD, NE	iCR, iPR, iSD, iUPD, iCPD, NE	iCR
iUPD	iPR	iPR, iSD, iUPD, NE	iPR, iSD, iUPD, NE, iCPD	iPR, iSD, iUPD, NE, iCPD	iPR
iUPD	iSD, NE	PR	iPR, iSD, iUPD, NE	iPR, iSD, iUPD, iCPD, NE	iPR
iUPD	iSD	iSD, iUPD, NE	iSD, iUPD, iCPD, NE	iSD, iUPD, ICPD, NE	iSD
iUPD	iCPD	Anything	Anything	Anything	iCPD
iUPD	iUPD	iCPD	Anything	Anything	iCPD
iUPD	NE	NE	NE	NE	iUPD

- Table assumes a randomised study where confirmation of CR or PR is not required.
- NE = not evaluable that cycle.
- Designation "I" for BOR can be used to indicate prior iUPD to aid in data interpretation.
- For patients with non-target disease only at baseline, only CR or non-CR/non-PD can be assigned at each TPR but is not shown in the table for ease of presentation.

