### **7.8.3 Best overall response, objective response, and disease control rate (DCR)**

OR is defined as the best overall response during the whole study period equal to PR or complete response (CR) according to RECIST [Eisenhauer et al] or as best overall response during the whole study period equal to immune partial response (iPR) or immune complete response (iCR) according to iRECIST. No confirmation of PR/CR and iPR/ iCR is required.

The ORR [%] is defined as the relative number of patients achieving OR according to iRECIST/RECIST in the respective cohort. The DCR [%] is defined as the relative number of patients achieving at least one assessment of iCR, iPR, or iSD according to iRECIST in the respective cohort or as the relative number of patients achieving at least one assessment of CR, PR, or SD according to RECIST.

The ORR/DCR according to iRECIST/RECIST will be summarized with two-sided 95% exact Clopper-Pearson CIs for binomial proportions by cohort.

The best overall response according to RECIST will be summarized by cohort, using the following categories and hierarchy: OR (RECIST) with subcategories CR and PR, SD, PD, not evaluable.

The best overall response according to iRECIST will be summarized by cohort using the following categories and hierarchy: OR (iRECIST) with subcategories iCR, iPR, iSD, iUPD, iCPD, not evaluable.

The disease control according to RECIST will be summarized by cohort, using the following categories and hierarchy: disease control (RECIST) with subcategories CR, PR, and SD, and PD, not evaluable.

The disease control according to iRECIST will be summarized by cohort using the following categories and hierarchy: disease control (iRECIST) with subcategories iCR, iPR, and iSD, and iUPD, iCPD, not evaluable.

The maximal shrinkage in tumor burden (i.e. maximal percentage decrease in sum of longest diameter compared to baseline = relative change from baseline) will be displayed

in a waterfall plot. The bars will be colored according to best overall response according to RECIST/iRECIST. Two different colors will be used for PD with new lesion and PD without new lesion. iUPD and iCPD will have the same color. Waterfall plots will be provided for Cohort 2A, Cohort 2B, Cohort 2, non-randomized, for Cohort 3A, Cohort 3B, Cohort 3, and Cohort 2A-I, Cohort 2A-II, and Cohort 2A-III, randomized, and for patients fulfilling and not fulfilling extended in/exclusion criteria (see Section 6.6) of Cohorts 2A, non-randomized.

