#### **7.8.6 Progression-free survival (PFS) and overall survival (OS)**

According to RECIST, PFS is defined as the period from the first dose of study drug until PD or death from any cause (whatever occurs first).

PFS is defined as the period from the first dose of study drug until the first time one of following events occurs

- Progression criteria according to iRECIST/RECIST met

- Start of non-trial systemic anti-cancer treatment (which is regarded as progression according to the protocol).
- death from any cause [REDACTED] after last post-baseline CT assessment [REDACTED] after first dose of study drug, if no post-baseline CT assessment is available.

Non-trial systemic anti-cancer treatment is defined as concomitant or post-study treatment/medication that is classified as chemotherapy in the eCRF. Mitotane therapy is not considered as non-trial system anti-cancer treatment.

According to RECIST the progression criteria is met at the first date of post-baseline CT assessment with PD documented as response, if not more than one scheduled CT assessment is missing or not evaluable before this CT assessment and the previous CT assessment was performed within [REDACTED] to this CT assessment.

According to iRECIST the progression criteria is met at the date of CT assessment with response documented as iUPD for that the next CT assessment documents iCPD as response (without any intervening assessments with other outcome), i.e. PD is confirmed, and if not more than one scheduled CT assessment is missing or not evaluable before the CT assessment with iUPD documented and the previous CT assessment was performed within [REDACTED] to CT assessment with IUPD documented. If progression is not confirmed and there is no subsequent CT assessment with iSD, iPR or iCR as response then the iUPD date will still be used as date of progression met in the following scenarios:

- no further response assessments are done or
- the next timepoint responses are all iUPD, and iCPD never occurs.

Non-trial systemic anti-cancer treatment is defined as concomitant or post-study treatment medication that is classified as chemotherapy in the eCRF. Mitotane therapy is not considered as non-trial system anti-cancer treatment.

Patients without an event as defined above will be censored based on the rules in Table 3.

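### SAP 7.8.3 lists iUPD above iCPD for iRECIST best overall response; applied as a ranking, this tabulates confirmed progressors who never had iSD or better as unconfirmed, contrary to Protocol Table 9

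*SAP*

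**What the plan says.** SAP 7.8.3 summarises iRECIST best overall response by cohort under "categories and hierarchy: OR (iRECIST) with subcategories iCR, iPR, iSD, iUPD, iCPD, not evaluable". The iRECIST disease-control summary keeps the same order: "disease control (iRECIST) with subcategories iCR, iPR, and iSD, and iUPD, iCPD, not evaluable". The visible SAP text gives no other algorithm for deriving best overall response from time-point responses, and it does not cite Protocol Table 9.

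Protocol Section 12.1 (Confirming Progression) says: "Unlike RECIST 1.1, iRECIST requires the confirmation of progression and uses the terms iUPD (unconfirmed progression) and iCPD (confirmed progression". SAP 7.8.6, defining iRECIST progression for PFS, likewise describes a scan with "response documented as iUPD for that the next CT assessment documents iCPD as response".

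For best overall response the protocol has its own rule. Under Table 8 it says: "All patients will have their iBOR from the start of study treatment until the end of treatment classified as outlined below". What follows is "Table 9 : iRECIST best overall response", which contains the row "iUPD iCPD Anything Anything Anything iCPD" (five time points, then the iBOR). The next row gives iCPD for iUPD, iUPD, iCPD.

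**The concern.** A hierarchy for a best-response variable is normally read as a ranking: take the highest category the patient ever reached. The parallel RECIST 1.1 list in SAP 7.8.3 (CR, PR, SD, PD, not evaluable) works correctly in that way. SAP 7.8.3 also defines response as the best over the whole study period, and disease control as at least one qualifying assessment. A programmer would reasonably treat the iRECIST list likewise.

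The iRECIST list does not work that way, because its two progression categories are successive stages of one process and the earlier stage is ranked higher. A table built on it would suggest that no patient had confirmed progression as best response, in a trial where confirmed iRECIST progression is a reason to stop treatment (Protocol 4.2 and 5.3.3).

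In the visible text, these two tables are the only planned aggregate summaries that separate confirmed from unconfirmed progression as best response. The waterfall plots give both one colour (SAP 7.8.3), and the 6-month table puts both in one subcategory (SAP 7.8.2).

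**Working it through.** There is no plan figure to reproduce. The check compares the two rules on possible sequences of assessments. All counts below are counts of sequences, not patient frequencies.

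**Step 1: logic.** Number the SAP order iCR = 1, iPR = 2, iSD = 3, iUPD = 4, iCPD = 5, NE = 6, and define best response as the smallest number reached. Any patient with an iCPD (5) also has an earlier iUPD (4), so the minimum is at most 4. The value 5 is never returned.

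**Step 2: Protocol Table 9, row by row.** Each row was expanded into all the sequences it allows. The entry printed as PR in row 4 was read as iPR, and Anything as any of the six categories.

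| Row | Table 9 iBOR | Sequences | SAP order used as a ranking |
|---|---|---|---|
| 1 | iCR | 16 | 16 iCR |
| 2 | iCR | 90 | 90 iCR |
| 3 | iPR | 100 | 100 iPR |
| 4 | iPR | 40 | 40 iPR |
| 5 | iSD | 48 | 48 iSD |
| 6 (iUPD, iCPD, then anything) | iCPD | 6³ = 216 | 91 iCR, 61 iPR, 37 iSD, 27 iUPD, 0 iCPD |
| 7 (iUPD, iUPD, iCPD, then anything) | iCPD | 6² = 36 | 11 iCR, 9 iPR, 7 iSD, 9 iUPD, 0 iCPD |
| 8 | iUPD | 1 | 1 iUPD |

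Six rows agree. The two rows that should give iCPD never do.

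**Step 3: who is affected.** Take every sequence of 2 to 5 assessments that ends at a first iCPD directly after an iUPD. Earlier assessments can be iCR, iPR, iSD, iUPD or NE.

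- All such sequences: 1 + 5 + 25 + 125 = 156.
- Earlier assessments only iUPD or NE: 1 + 2 + 4 + 8 = 15. The SAP order returns iUPD.
- Allowing iSD as well: 1 + 3 + 9 + 27 = 40, so 40 − 15 = 25 return iSD.
- Allowing iPR as well: 1 + 4 + 16 + 64 = 85, so 85 − 40 = 45 return iPR.
- The remaining 156 − 85 = 71 return iCR.

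None of the 156 returns iCPD. The 15 without iSD or better are the misclassified kind. The other 141 (25 + 45 + 71) take the better category, as Table 9 also does in the rows where iCR, iPR or iSD came before an iCPD.

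**Step 4: would swapping the two categories do?** With iCPD above iUPD, all 15 become iCPD. In rows 6 and 7, the 27 and 9 sequences without a later iSD or better also become iCPD. But 216 − 27 = 189 sequences in row 6 and 36 − 9 = 27 in row 7 still disagree with Table 9, because a best-of ranking lets an assessment after iCPD improve the result. SAP 7.8.1 admits assessments made after study treatment, so such sequences can arise.

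**Step 5: what does not use this order.** ORR counts iCR and iPR. DCR counts patients with at least one iCR, iPR or iSD. Time-to-OR, DOR and PFS follow their own definitions (SAP 7.8.4 to 7.8.6). The 6-month primary endpoint treats iUPD and iCPD together as progression (SAP 7.8.2).

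**The case against.** The strongest reply is that the list describes table layout. The same sentence form appears four times in SAP 7.8.3. A composite heading with subcategories looks like nested rows, most clearly in the disease-control sentences. The SAP never says that iBOR is the highest-ranked time-point response. The protocol already supplies Table 9 and says that time-point and best overall responses are recorded separately, and the SAP states that it reflects Protocol version 5.0. A table built from the recorded or Table 9 iBOR would have a populated iCPD row. The mock-up tables are in SAP Appendix II, which is not available here, and SAP 5.3 on changes to planned analyses is redacted.

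This stands as a possible reading, so an empty row is not certain. It does not remove the problem. The SAP uses the word hierarchy, and its visible text names neither Table 9 nor the recorded iBOR as the source. Followed as written, it gives a result the protocol contradicts.

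It is also fair to say that little is lost for good: SAP 7.8.3 lists all response assessments, so confirmation status can be recovered patient by patient.

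**Conclusion.** The concern holds in limited form. If the SAP 7.8.3 order is applied as a best-of ranking, which is its natural but not its only reading, the iCPD row is empty, and confirmed progressors with no iSD, iPR or iCR appear as iUPD. That contradicts Protocol Table 9. It affects the iUPD/iCPD split in the iRECIST best-overall-response and disease-control tables, both descriptive and secondary. It is worth correcting but does not touch the trial's main conclusions.

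A reader might infer that every confirmed progressor would be shown as unconfirmed. The documents do not support that: a patient with iSD or better before confirmation is tabulated in that better category, and Table 9 does the same.

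A reader might also size the effect from the 48% disease control rate that Protocol 1.2 cites for avelumab. Its complement, 52%, does not count misclassified patients. It can include non-evaluable patients and patients whose progression was never confirmed, who are correctly iUPD. The documents give no basis for a patient count.

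**What to change.** Add to SAP 7.8.3:

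- iBOR is derived by Protocol Table 9. An iCPD replaces an earlier iUPD when no iSD, iPR or iCR came before confirmation. iUPD is assigned only if progression was never confirmed and no iSD or better followed. Assessments after iCPD cannot improve iBOR.
- The listed categories give row display order only.
- The same rule applies to the iRECIST disease-control table.

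If the tables are meant to use the separately recorded iBOR, say so and check it against Table 9.

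Two related points should be settled in the same edit. The protocol's iBOR runs to the end of treatment, whereas SAP 7.8.3 uses the whole study period, so one window should be named. The SAP should also say whether an iSD or better after iCPD counts toward ORR and DCR, since the SAP definitions would admit it and Table 9 would not.

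The cost is a few lines of text and one derivation step in programming. No new data are needed.

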#### **7.8.4 Time-to-OR**

Time-to-OR using RECIST criteria is defined as the period from the first dose of study drug until PR or CR, whichever comes first. Patients without PR or CR (RECIST) will be right-censored at the time of progression (the same time point as the event time point for PFS according to RECIST, see Section 7.8.6). If no progression occurred, patients will be right-censored following the same censoring rules as for PFS (see Section 7.8.6).

Time-to-OR using iRECIST is defined as the period from the first dose of study drug until iPR or iCR, whichever comes first. Patients without iPR or iCR (iRECIST) will be right-censored at the time of progression (the same time point as the event time point for PFS according to iRECIST, see Section 7.8.6). If no progression occurred, patients will be right-censored following the same censoring rules as for PFS (see Section 7.8.6).

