**Table 3 Censoring rules for PFS**

Situation	Date of Event or Censoring
No CT assessment at baseline	Date of first study treatment administration
No progression nor death nor non-trial systemic anti-cancer treatment documented	Date of last post-baseline CT assessment
Death more than [REDACTED] after last post-baseline CT assessment	Date of last post-baseline CT assessment
Death more than [REDACTED] after first study treatment and without post-baseline CT assessment	Date of first study treatment administration
Progression criteria met after $\geq 2$ consecutive schedule missing CT assessments	Date of last post-baseline CT assessment before missing CT assessment
Progression criteria met [REDACTED] after previous CT assessment	Date of previous CT assessment

OS is defined as the period from the first dose of study drug until death due to any cause.

Patients alive at their last visit will be censored at the last visit date.

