### 7.8.7 Analyses of DOR, time-to-OR, PFS and OS endpoints

DOR, DDC, time-to-OR, PFS and OS will be described by KM plots along the number of patients at risk. Separate plots will be created including the curves of following cohorts:

- Cohorts 2A, 2B, 3A, and 3B, non-randomized
- Cohorts 2A, 2B, and 2, non-randomized
- Cohorts 3A, 3B, and 3, non-randomized
- Cohort 2A-I, Cohort 2A-II, and Cohort 2A-III, randomized
- For patients fulfilling and not fulfilling extended in/exclusion criteria of Cohorts 2A, non-randomized

The number of patients with an event of interest and being censored and the median, as well as 1st and 3rd quartiles of the estimated times of interest will be presented with their associated two-sided 95% CIs according to Klein and Moeschberger using a log-log-transformation. If reasonable, non-parametric competing risks techniques will be applied for time-to-OR as a sensitivity analysis, if a non-negligible number of deaths is recorded without earlier objective responses. For PFS and OS, 6-months, 12-months, 18-months, and 24-months PFS/survival estimates and corresponding 95% pointwise confidence limits will be provided in addition.

If the number of events is sufficient, DOR, time-to-OR, PFS and OS will be analyzed using Cox proportional hazards model. For Cohort 2 and 3, non-randomized, the following covariates will be included in the Cox-proportional hazards model

- Primary diagnosis (ACC vs. MPP)
- Previously treated (yes vs. no).

For cohort 2, randomized, the variable cohort (Cohort 2A-I, Cohort 2A-II, vs Cohort 2A-III) will be included in the Cox-proportional hazards model as covariate. No Cox-proportional hazard models will be provided for by patients fulfilling and not fulfilling extended in/exclusion criteria of Cohorts 2A, non-randomized.

All results of the CT scans will be listed.

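### Time to response is estimated by Kaplan-Meier with non-responders censored at their PFS event, which overstates how many patients respond and can print quartiles or a median that too few responders support

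*SAP*

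**What the plan says.** SAP 7.8.4 measures time to objective response from the first dose. For non-responders it states: "Patients without PR or CR (RECIST) will be right-censored at the time of progression". It ties that time to the PFS event time in 7.8.6, applies the PFS censoring rules where there is no progression, and repeats all this for iRECIST. Nothing restricts the analysis to responders; duration of response in 7.8.5, by contrast, is restricted to them.

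SAP 7.8.6 counts as PFS events progression, the start of non-trial systemic anti-cancer treatment, and death within a blacked-out window. Table 3 censors later deaths at the last CT. A death beyond a blacked-out interval "after first study treatment and without post-baseline CT assessment" is censored at first dose. Progression after two or more consecutive missed scheduled CTs goes to "Date of last post-baseline CT assessment before missing CT assessment".

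SAP 7.8.7 prescribes Kaplan-Meier plots with numbers at risk. The tabulated results are "The number of patients with an event of interest and being censored and the median", with first and third quartiles and 95% confidence intervals. On competing risks it says: "If reasonable, non-parametric competing risks techniques will be applied for time-to-OR as a sensitivity analysis", and then only "if a non-negligible number of deaths is recorded without earlier objective responses".

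**The concern.** Censoring in Kaplan-Meier assumes that the censored patient stays exposed to response at the same rate as those still followed. A patient who has died cannot respond, and one who has progressed or moved to other systemic therapy is not exchangeable with patients still on study without progression. As soon as one response follows such an exit, 1-KM exceeds the proportion of the cohort that has responded.

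The safeguard in 7.8.7 does not cure this. It leaves the main Kaplan-Meier quartiles in place, it is discretionary, and it does not name progression or non-trial therapy as competing events.

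There is a second, smaller defect under RECIST 1.1. Whether a progressor is censored depends on the future: one who later responds stays at risk, and one who never responds leaves at progression. Protocol 4.2 allows treatment beyond RECIST 1.1 progression, so this can happen. For iRECIST it is largely handled. Apart from a confirmed iUPD, 7.8.6 lets the iUPD date stand only under this condition: "If progression is not confirmed and there is no subsequent CT assessment with iSD, iPR or iCR as response".

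At stake is a report that gives a time by which 25% or 50% of a cohort had responded when fewer ever did, beside an objective response rate (ORR) that says otherwise.

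**Working it through.** The plan states no expected value for time to response, so there is no figure of its own to reproduce. The check compares 1-KM with the true proportion of responders on the background counts in Protocol 1.2.

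**Inputs**
- Pembrolizumab trial in ACC: 39 patients, 9 PR, 7 SD, so 39 - 9 - 7 = 23 others. Time to PR: median 4.1 months, range 1.7-10.5.
- Avelumab trial in ACC: 50 patients, 3 PR, 21 SD, so 26 others. Response times are not given.
- CTs at weeks 9, 17 and 25, then every 8 weeks (SAP 7.8.1). Cohort sizes 26 (2A, non-randomized) and 13 (2A-I) (SAP 4.2).

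**Set-up.** Of n patients, R respond, k of them at the week 9 CT. The n - R - s patients with neither response nor SD leave at that CT, after its responses are counted. The s patients with SD stay to the end. This is the least biased arrangement: earlier exits, or SD patients progressing between later responses, shrink the risk sets and raise 1-KM.

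**Formula.** At week 9 the curve is (n - k)/n, and R + s - k patients remain. The other R - k responses come one at a time, and the product telescopes:

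final 1-KM = 1 - (n - k)/n × s/(R + s - k)

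**Range of k, pembrolizumab counts.** At 30.5 days per month, the earliest PR is at 1.7 × 30.5/7 = 7.4 weeks, so k is at least 1. The fifth of nine, the median, is at 4.1 × 30.5/7 = 17.9 weeks, so k is at most 4. For n=39, k=1: 1 - 38/39 × 7/15 = 54.5%.

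| n, R, s | k | final 1-KM | ORR |
|---|---|---|---|
| 39, 9, 7 | 1, 2, 3, 4 | 54.5, 52.6, 50.3, 47.6% | 23.1% |
| 50, 3, 21 | 0, 1, 2, 3 | 12.5, 10.5, 8.4, 6.0% | 6.0% |
| 26, 6, 5 | 1, 2, 3 | 51.9, 48.7, 44.7% | 23.1% |
| 26, 2, 11 | 0, 1, 2 | 15.4, 11.9, 7.7% | 7.7% |
| 13, 3, 2 | 1, 2 | 53.8, 43.6% | 23.1% |

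The last three rows scale the two sets of proportions to this trial's cohorts; their k, like that for the avelumab counts, is assumed. If all responses fall at the first CT (k = R), the formula gives R/n and there is no bias.

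**Quartile and median (39, 9, 7).** 1-KM passes 25% at the fifth response (k = 1, 2) or the sixth (k = 3, 4). It passes 50% at the ninth response for k = 1 to 3, with 8 patients at risk, and never for k = 4. The avelumab counts give no quartile or median.

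**Cumulative incidence on the same counts.** With the 23 coded as competing events, Aalen-Johansen ends at 9/39 = 23.1% for every k. If d of the 23 were instead censored at first dose under Table 3, it would end at 9/(39 - d): 23.7% (d = 1), 25.0% (d = 3), 26.5% (d = 5). The value of d is assumed.

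**Cross-check by simulation.** 5,000 replicates were run with exponential cause-specific hazards, this trial's CT schedule, and the background median PFS as the median time to the competing event: 2.1 months for response rates of 23.1% and 15% (the latter assumed), 2.6 months for 6%. For n = 26, mean final 1-KM against cumulative incidence was 52% against 23%, 38% against 15%, and 17.5% against 6%. Kaplan-Meier gave a first quartile although fewer than 25% responded in 44%, 50% and 22% of replicates.

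**The case against.** **The SAP already provides a competing-risks analysis.** It does, and its trigger includes patients who progress and later die, so it may well be met in ACC. In MPP it is slower to be met, with median survival of about 6-7 years (Protocol 1.3.5), but Cohort 3 enrols patients with documented progression and survival follow-up is long. This narrows the point to main against sensitivity analysis, the discretion, and the unnamed competing events. Those remain.

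**Most of the figures are curve heights, which are not tabulated for this endpoint.** That is right: landmark estimates are planned only for PFS and OS. The quartiles and median are tabulated, however. The event counts printed with them and the ORR beside them let a careful reader see the mismatch, but do not correct it.

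**Death as a censoring time is inferred.** It follows from the tie to the PFS event time, and Table 3 moves some deaths to an earlier date. The inference is reasonable, and the deaths trigger in 7.8.7 fits it.

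**Responses after other therapy are a narrow route.** SAP 7.8.1 counts assessments made after study treatment, but leaves CTs that follow anti-cancer therapy given before treatment termination to the data review meeting. Protocol Appendix 1 takes best response only to the end of treatment, whereas SAP 7.8.3 uses the whole study period. Such responses may be few and their handling is unsettled, which is a reason to show them separately.

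**The size depends on assumptions.** It does. Whether the median is crossed is fragile: it is not at k = 4 for n = 39, nor at k = 2 or 3 for n = 26 with 6 responders. In arms of 2 and 4 patients neither curve informs.

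**Conclusion.** The concern holds, as a minor one. Followed exactly, the plan can report a first quartile or median time to response that too few responders support. The direction is certain: 1-KM is never below the cumulative incidence, and exceeds it once a response follows a competing event. The size runs from nothing (all responses at the first CT) to about double the response rate or somewhat more on the pembrolizumab counts. It rests on background response rates, assumed response timing, and all patients without response or SD leaving by the first CT.

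No decision depends on this endpoint. The ORR with its exact interval and the 6-month PFS rate are unaffected, numbers at risk and censored are shown, and all response assessments are listed.

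**What to change.** - **SAP 7.8.7:** make the Aalen-Johansen cumulative incidence of response the main description, and delete the discretionary wording and the deaths trigger.
- **SAP 7.8.4:** classify each patient by whichever comes first, response or a competing event: progression by the criteria in use, death, or start of non-trial systemic therapy. For this endpoint, count the deaths and late progressions that Table 3 censors for PFS as competing events. Censor only patients alive, progression-free and without response, at their last CT. This also removes the dependence on later response under RECIST 1.1.
- **Late responses:** show any first response after RECIST progression or after non-trial therapy separately, so that a difference from the ORR in 7.8.3 is explained.
- **Summary:** replace the Kaplan-Meier median and quartiles for time to response with the median and range among responders, beside the ORR.
- **Cox model:** it can stay, read as a cause-specific hazard of response.

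The cost is SAP wording, one event code and a little programming; the SAP already names competing-risks techniques. The curve will look less favourable, and may end slightly below the ORR if some responses come after progression or other therapy.
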